9.5. Statistical Method

9.5.1. General methods

Data collected in the study will be documentedwith summary tables and patients data listings. Continuous variables will be summarized with descriptive statistics (the number of patients, mean, median, standard deviation, minimum and maximum). Categorical variables will be summarized with frequency and proportion. Time-to-event datawill be summarized via Kaplan-Meier (KM) methodology using the 25th, 50th (median), and 75th percentiles with associated 2-sided 95% confidence intervals.

Unless specified otherwise, baseline measurement values should be the latest values prior to the first dose of the investigational drug. If the assessement is not available, the last assessment before the visit will be used.

Medical history, AEs and concomitant treatment procedures will be coded with Medical Dictionary for Regulatory Activities (MedDRA). Past and concomitant medications will be coded according to the World Health Organization Drug Dictionary.

Unless specified otherwise, Ex11 ITT population and ITT population are used for efficacy analysis (primary endpoint and secondary endpoint) and safety population is used for safety analysis.

Zai Lab

9.5.2. Patients disposition

Disposition of all patients entering the study (patients who sign the informed consent form of the study and meet the inclusion criteria and don't meet the exclusion criteria) will be summarized. The number of patients in each population (safety, PK, Ex11 ITT, ITT, Ex11 PP, PP, if applicable) and the number of patients excluded from each population will be displayed. The number and proportion of patients who complete the study, as well as those who discontinue the studywill be summarized along with the reason for discontinuation.

9.5.3. Demographic data and baselinecharacteristics

Demographic and baseline characteristics (including recurrence risk evaluation at enrollment) will be summarized.

Medical history will be summarized for the safety population.

9.5.4. Extent of exposure

Total subjects who receive treatment with the investigational drug will be summarized with n and percentage. Moreover, continuous descriptive statistics will be used to display number of treatment cycles subjects received. These analyses will be performed for the safety population.

9.5.5. Efficacy analysis

9.5.5.1. Primary endpoint: progression-free survival

The primary endpoint PFS is defined as the time interval from randomization to the earliest documented evidence of progressive disease based on assessment of the independent radiology review or death due to any causes. PFS analysis in the ITT population will be stratified by the randomization stratification factors (KIT exon 11 mutation; KIT exon 9 mutation; other (KIT/PDGFRA WT or other KIT [lacking exon 9 or 11]/PDGFRA mutation). Survival curve of different treatment groups will be plotted with KM method and the median progression-free survival (mPFS) and its 95% CI of different groups will be calculated. Under a two-sided significance level of 0.05, stratified log-rank test will be adopted to compare difference in survival curve between the two groups. Point estimate of hazard ratio will be obtained by stratified Cox regression model and relevant 95% CI will be calculated with Wald method. Randomization stratification factor is stratification factor and treatment factor is the covariant.

Rules of defining PFS events and censoring PFS will be elaborated in the statistical analysis plan (SAP). Sensitivity analysis for PFS will be specified in the SAP.

ITT population will be used as the primary analysis population in this analysis while the PP

population as supportive analysis population. Sensitivity analysis of progression-free survival will be performed, which will be further described in SAP.

Zai Lab

9.5.5.2. Secondary efficacy endpoints

9.5.5.2.1. Analysis of objective response rate

ORR is defined as the proportion of patients, which is confirmed as CR or PR, based on independent radiology review. ITT population will be used as the primary analysis population in this analysis while the PP population as supportive analysis population. Patients with unknown or missing response will be considered non-response, that is, they will be included in the denominator when calculating proportion. Rate difference of objective response rate (ORR) between treatment groups with 95% CI will be calculated with stratified Miettinen and Nurminen and statistical test will be performed

Overall survival 9.5.5.2.2.

OS is defined as interval, the time from randomized allocation to patient death because of any cause. Surviving patients or those lost to follow-up will be censored on the contact day of the last assessment. Model similar to that for PFS analysis will be used for OS analysis.

9.5.5.2.3. Disease control rate

Disease control is defined as patients who obtained CR, PR or SD. DCR will be summarized according to n and proportion. Rate difference of disease control rate (DCR) between treatment groups and 95% CI will be calculated with stratified Miettinen and Nurminen and statistical test will be performed.

9.5.5.2.4. Investigator-assessed progression-free survival

Investigator-assessed PFS is defined as the time interval from randomization to the earliest documented evidence of progressive disease based on assessment of the investigator or death due to any causes. Differences between treatment groups will be assessed with the same method as the primary endpoint.

9.5.6. **Safety Analysis**

9.5.6.1. AEs

AEs in the safety population will be summarized with the number of events and proportion of patients according to system organ class (SOC) and preferred term. All tables will only include TEAE. "Treatment emergent" is defined as any AEs occurring during the first dose of the investigational drug and up to 30 days after the last dose of the investigational drug. However, the listing will include all AEs collected.

Toxicity grade of AE will be classified with NCI-CTCAE V5.0 (See Table 12). If a patient has the same SOC or preferred term evet for several times, only the most severe event will be summarized in the tables for that SOC and preferred term. AEs grade ≥ 3 will be summarized. Missing toxicity grade will not be imputed.

SAEs, AEs and AESIs that lead to dose reduction or discontinuation and AEs will be also analyzed.

Formal hypothesis test of incidence of AE will not be performed.

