2.2. Secondary objective

- To assess objective response rate (ORR) by independent radiologic review using RECIST v1.1-GIST-specific criteria
- To assess disease control rate (DCR) by independent radiologic review
- To assess PFS based on Investigator assessment
- To assess overall survival (OS)
- To compare the safety profile of DCC-2618 (ripretinib, ZL-2307) to the safety profile of sunitinib
- To assess pharmacokinetic characteristics of DCC-2618 (ripretinib, ZL-2307)

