8.2. End of Study

The main reason for termination or withdrawal form the study should be confirmed according to the following classification:

- Death
- Lost to Follow-up
- Termination of the study by the sponsor
- Patients will withdraw from the study

Patient withdrawal and replacement 8.3.

Patients will be not substituted in the study.

9. Statistical Consideration

9.1. **Determination of sample size**

This study will bridge foreign clinical trial (study INTRIGUE) to prove the efficacy of the investigational drug DCC-2618 (ripretinib, ZL-2307) is consistent in foreign population and Chinese population. In the study, no statistical test hypothesis is specified in advance. Statistical significance test for efficacy endpoint and multiplicity correction for multiple analysis populations will not be performed.

Approximately 98 subjects will be enrolled into the study and randomized to a test group and a control group in a 1:1 ratio. The sample size eatimation will be based on the same study hypothesis as foreign, that is, median progression-free survival (mPFS) is 9 months in the test group and 6 months in the control group. Hazard ratio (HR) of the test group to the control group is 0.667. If the study keeps \geq 50% of the overall effect size of study INTRIGUE, that is, point estimate of HR should be ≤ 0.833 , it will be considered that results of this study are consistent with those of study INTRIGUE. If 58 cases of PFS events occur, a 80% probability will be obtained and athe conclusion of consistency will be drawn with a probability of 80%. Assumeing the subjects annual drop-out rate of subjects of the total study population is 5%, approximately 98 subjects (49 for the test group and the control group, respectively) are enrolled within 7 months and followed up for 7 months, and 58 cases of PFS events will occur. Main Primary analysis based on ITT will be carried outperformed when 58 cases of PFS events occur and it is estimated that the data cutoff of the analysis will be 7 months after completing enrollment.

Zai Lab

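### Section 9.5.6.1 plans only crude AE counts and proportions, with no time-based summary to support the safety comparison if ripretinib patients are treated for longer

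*Combined protocol and SAP*

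**What the plan says.** Section 2.2 lists among the secondary objectives "To compare the safety profile of DCC-2618 (ripretinib, ZL-2307) to the safety profile of sunitinib".

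Section 9.5.6.1 gives the AE method: "AEs in the safety population will be summarized with the number of events and proportion of patients", by system organ class and preferred term. It adds summaries by worst grade, of grade 3 or higher events, and of SAEs, AESIs and AEs leading to dose reduction or discontinuation. Treatment-emergent events run from the first dose "up to 30 days after the last dose of the investigational drug", so the window lengthens with treatment. The section states that "Formal hypothesis test of incidence of AE will not be performed".

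Section 9.5.4 reports exposure separately: the number treated, and "continuous descriptive statistics will be used to display number of treatment cycles subjects received". Nothing links exposure to the AE tables. The documents plan no exposure-adjusted rate, time to first AE, cumulative incidence or fixed-window comparison. Section 9.5.5.1 leaves PFS censoring rules and sensitivity analyses to the SAP, but section 9.5.6.1 makes no such reference for AEs.

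Under section 3.3, treatment continues to independently confirmed progression, intolerable toxicity or withdrawal of consent. Section 9.1 assumes that "median progression-free survival (mPFS) is 9 months in the test group and 6 months in the control group".

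**The concern.** With treatment to progression, the arm with longer PFS is also observed for AEs for longer. Event counts grow with observation time, and so does the proportion of patients with at least one event. Two drugs with the same monthly AE rate would then show different crude figures, and the planned tables would not tell a higher rate from a longer window. What is at stake is how the section 2.2 safety comparison is read, not the primary analysis.

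**Working it through.** **Inputs from the documents.** Section 9.1: PFS medians 9 and 6 months, HR 0.667, threshold 0.833, 58 events, 49 per arm, 5% annual dropout, 7 months of enrolment plus 7 months of follow-up (cutoff at month 14). Section 3.3: study end no later than 20 months after enrolment (month 27). Section 9.5.6.1: 30-day tail.

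**Assumptions.** Exponential PFS and dropout; uniform enrolment; treatment ends only at a PFS event or dropout; the same constant AE hazard λ in both arms. The documents give no AE hazard for this comparison, so a range of 0.03 to 0.10 per month is shown.

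**Step 1: the plan's own figure.** Probability that the observed HR is at or below 0.833 = Φ[(ln 0.833 − ln 0.667) × √(58/4)] = Φ(0.222 × 3.81) = Φ(0.846) = 80.1%, against 80% stated. Expected events at month 14 are 26.4 + 33.4 = 59.8, against 58 stated. The planning model is reproduced closely enough to use for exposure.

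**Step 2: time on treatment.** Dropout hazard = −ln(0.95)/12 = 0.0043 per month. Hazard of leaving treatment: h = ln2/9 + 0.0043 = 0.0813 (ripretinib) and ln2/6 + 0.0043 = 0.1198 (sunitinib). For a patient followed u months, mean exposure is (1 − e^(−hu))/h, averaged over u from 7 to 14 months (month-14 cutoff) or 20 to 27 months (month 27).

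- Month 14: 6.99 versus 5.90 months, ratio 1.18.
- Month 27: 10.46 versus 7.83 months, ratio 1.33.

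**Step 3: add the 30-day tail.** The window is min(T + m, u), where T is time on treatment and m = 30 days = 0.986 months. Its mean is m + (1 − e^(−h(u−m)))/h, averaged over u.

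- Month 14: 7.53 versus 6.58 months, ratio 1.14.
- Month 27: 11.29 versus 8.75 months, ratio 1.29.

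**Step 4: crude incidence at equal λ.** On treatment only, incidence is λ/(λ+h) × (1 − e^(−(λ+h)u)), averaged over u. With the tail it is 1 − E[e^(−λW)], where W is the Step 3 window. The standard error (SE) is √[p₁(1−p₁)/49 + p₂(1−p₂)/49], for the figures with the tail. Incidences are ripretinib versus sunitinib.

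| Cutoff | λ per month | On treatment only | With 30-day tail | SE (points) |
|---|---|---|---|---|
| Month 14 | 0.03 | 18.4% vs 15.7% (2.7 points) | 19.8% vs 17.5% (2.3) | 7.9 |
| Month 14 | 0.10 | 46.4% vs 40.5% (5.9) | 49.9% vs 45.0% (4.9) | 10.1 |
| Month 27 | 0.03 | 24.9% vs 19.4% (5.5) | 26.9% vs 21.7% (5.2) | 8.6 |
| Month 27 | 0.10 | 54.3% vs 45.2% (9.1) | 58.5% vs 50.3% (8.2) | 10.0 |

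Section 7.10 stops AE reporting when new anti-tumor therapy starts, so the tail may be cut short. The two incidence columns therefore bracket the expected excess.

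**Step 5: early-onset AEs.** Let the hazard act only in cycle 1 (42 days, 1.38 months) and be zero afterwards. On treatment only, crude incidence is 22.9% versus 22.3% at λ = 0.2, and 40.3% versus 39.4% at λ = 0.4, so the excess is under 1 point. With the tail it is under 0.1 point.

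**Step 6: how an exposure-adjusted rate behaves.** The rate is first events divided by patient-months at risk. With a constant equal hazard its ratio is 1.00, as it should be. In the cycle-1-only case with the tail, its ratio (ripretinib to sunitinib) is about 0.88 at month 14 and 0.78 at month 27, although the true risk is equal.

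**The case against.** A reader might infer that the planned comparison is biased against ripretinib. The documents do not support that as an unconditional statement. They give no expected treatment duration; longer ripretinib exposure is inferred from the PFS medians and the treat-to-progression rule. Section 3.3 also ends treatment for intolerable toxicity, which the calculation leaves out. An extra ripretinib discontinuation hazard of 0.1198 − 0.0813 = 0.0385 per month would remove the exposure difference altogether. Background medians of 41.7 weeks for second-line ripretinib (section 1.3.2.3) and 24.1 weeks for sunitinib (section 1.4) point the same way as the planning assumption, but they come from different studies.

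A reader might also infer that the skin AESIs are the events most affected. Table 1 does schedule more dermatology examinations for patients who stay on treatment longer, but the documents give no onset times for these events.

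Three further objections have weight:

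- The AE analysis is descriptive, and cumulative incidence over a treatment course is a legitimate description of what patients experience. It misleads only if read as a rate.
- Section 9.5.4 lets a reader see a difference in cycles and roughly scale event counts, though it does not give time at risk for first events.
- An exposure-adjusted rate alone can mislead the other way (Step 6).

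These points stand. They limit the size of the concern and shape the fix. They do not supply the missing time-based summary, and the absence of a test does not stop the arms from being compared under section 2.2.

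**Conclusion.** The gap is real but minor: a comparative safety objective rests on crude counts and proportions over a window that follows treatment duration. The calculated excess on ripretinib requires the 9 versus 6 month assumption to hold, similar toxicity discontinuation in the two arms, and AE hazards that are roughly constant over time. At month 14 it is well within one standard error. The month-27 figures are also below one standard error, and they apply only if the study runs to its latest permitted end. Where the assumptions do hold, the excess has the same sign for every AE term, so it would not average out across the tables.

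**What to change.** Keep the crude tables. Add to section 9.5.6.1, for any TEAE, grade 3 or higher AEs, SAEs and AESIs:

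1. Time to first event by arm, shown as cumulative incidence, or incidence within a fixed window from first dose.
2. Exposure-adjusted incidence rates (patients with a first event per patient-month at risk), with the between-arm rate difference and 95% CI.

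State beside the rates that they assume a roughly constant hazard and would favour the longer-treated arm for early-onset events, so they should be read with item 1 and not alone.

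The cost is a few extra descriptive tables from dates already collected. No design element, sample size or clinical rule changes.

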6.4. Follow-up

Patients will be contacted by telephone 30 (± 5) days after the last dose of the study drug for safety follow-up to evaluate AE, collect information of concomitant medications/other treatments and collect new information of anti-tumor therapy.

After that, patients will be contacted by telephone for OS follow-up to collect new information of anti-tumor therapy and OS data.

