6.11.12. Safety follow-up

AE follow-up should be carried out in all patients $30 (\pm 5)$ days after the last dose of the study drug to collect information of concomitant medications/other treatments and collect new information of anti-tumor therapy.

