7.9. Adverse Events of Special Interest (AESIs)

An AESI is an AE (serious or nonserious) of scientific and medical concern specific to study drug, for which ongoing monitoring and immediate notification by the Investigator to the Sponsor is required. Such AEs may require further investigation to characterize and understand them. AESIs may be added or removed during a study by a protocol amendment.

The following AEs are considered AESIs:

- Squamous cell carcinoma of skin
- Actinic keratosis
- Keratoacanthoma

7.10. **Adverse Events Reporting Period**

The AE (including SAEs and AESIs) reporting period begins from the time that the patient provides informed consent through and including 30 days after the last dose of the study drug, or until a new anti-tumor therapy is initated, which occurs first. For any SAEs or AESIs occurring after this reporting period, it will be reported only when a causal relationship between the SAEs or AESIs and study product is suspected by the study drug.

7.11. Adverse Event, Serious Adverse Event, and Adverse Event of Special Interest Reporting Requirements

Each patient must be carefully monitored for the development of any AEs. This information must be obtained in the form of non-leading questions (e.g. "How are you feeling?") and from signs and symptoms detected during each examination, observations of study personnel, and spontaneous reports from patients. All AEs (serious and non-serious) spontaneously reported by the patient and/or in response to an open question from study personnel or revealed by observation, physical examination or other diagnostic procedures must be recorded.

When possible, signs and symptoms indicating a common underlying pathology must be noted as 1 comprehensive event. Accompanying signs or symptoms (e.g. abnormal laboratory values) must not be reported as additional AEs. If a diagnosis is unknown, one or more symptoms may be reported as separate AEs. If an underlying diagnosis is subsequently determined for the reported symptom(s), then the reported symptom(s) term(s) must be revised to be "attributed" or "due" to the diagnosis.

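### The TEAE window runs to day 30 with no cut at new anti-tumour therapy, although 7.10 stops AE reporting there, so next-line toxicity can enter the randomised arm's tables

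*Combined protocol and SAP*

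**What the plan says.** Section 7.10 of the protocol sets the reporting period for all AEs. It starts at consent and runs "through and including 30 days after the last dose of the study drug, or until a new anti-tumor therapy is initated, which occurs first". There is one exception: "For any SAEs or AESIs occurring after this reporting period, it will be reported only when a causal relationship" to study drug is suspected.

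Three other places govern what the site does after the last dose, and none mentions a stop at new therapy:

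- The AE row of Table 1 runs from consent to the safety follow-up.
- Section 6.4 has patients telephoned 30 (± 5) "days after the last dose of the study drug for safety follow-up to evaluate AE". At the same call the site is to "collect new information of anti-tumor therapy".
- Section 6.11.12 states that "AE follow-up should be carried out in all patients", again at 30 (± 5) days.

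On the analysis side, 9.5.6.1 defines treatment-emergent by time alone, from first dose and "up to 30 days after the last dose of the investigational drug". There is no condition on new therapy or on causality. The AE tables are restricted to TEAEs, and the listing holds every AE collected.

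**The concern.** Consider a patient who stops study drug, starts another agent within the next 30 days, and then has an adverse event. Under 7.10 the event is outside the reporting period unless it is an SAE or AESI suspected to be due to study drug. Under Table 1, 6.4 and 6.11.12 it can be elicited and recorded at the day-30 call. Once recorded, 9.5.6.1 makes it a TEAE of the randomised arm.

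Two things follow. All-cause TEAE incidence, including the grade 3 or higher summary, can mix the toxicity of two drugs. Collection can also differ between sites that each follow a section of the same protocol. Comparing the safety profile with that of sunitinib is a stated secondary objective (section 2.2), with TEAE, SAE and AESI incidence as its endpoints (section 9.2.2.2), so the tables affected are the ones that serve that objective.

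**Working it through.** The plan gives no figure to reproduce. The check is a comparison of text, followed by an illustration.

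**1. End of window, section by section**

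| Place | Purpose | End of window | Stops at new therapy? |
|---|---|---|---|
| 7.10 | AE reporting period | Day 30 after last dose | Yes, except suspected study-drug SAEs/AESIs |
| Table 1, AE row | Collection | Safety follow-up | No |
| 6.4 | Collection | Contact at day 30 (± 5) | No |
| 6.11.12 | Collection, all patients | Contact at day 30 (± 5) | No |
| 9.5.6.1 | TEAE definition and tables | Day 30 after last dose | No |

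**2. Fate of one event.** Take a non-serious AE, not an AESI, that starts after new therapy but before day 30.

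- Site follows 7.10: not recorded, so not tabulated.
- Site follows Table 1, 6.4 or 6.11.12: recorded, and tabulated as a TEAE of the randomised arm.

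The same event in the same kind of patient therefore has two outcomes.

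**3. Does the plan expect switches in this window?** Yes. Section 7.10 has a rule for them, and 6.4 and the safety follow-up column of Table 1 ask about new anti-tumour therapy at the contact where AEs are evaluated.

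**4. Length of the mismatch for one switcher.** Let d be the days from last dose to new therapy. Days inside the TEAE window but outside the 7.10 period = 30 − d. The documents do not give d, so these values are assumed:

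- d = 7: 30 − 7 = 23 days
- d = 14: 30 − 14 = 16 days
- d = 21: 30 − 21 = 9 days

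To set this against the whole TEAE window, take the planning median PFS as a rough proxy for time on treatment (6 months ≈ 183 days, 9 months ≈ 274 days) and add 30 days. The range is 9/(274 + 30) = 3% to 23/(183 + 30) = 11% of that patient's window. This is a share of time, not of events.

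**5. Can the number of switchers be derived?** No. The nearest quantity is the expected number of PFS events. With exponential PFS, uniform accrual over 7 months, analysis at month 14, no drop-out and λ = ln 2 / median:

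P(event) = 1 − [exp(−7λ) − exp(−14λ)] / (7λ)

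- Sunitinib, median 6: 1 − (0.4454 − 0.1984)/0.8087 = 69.5%, × 49 = 34.0
- Ripretinib, median 9: 1 − (0.5833 − 0.3402)/0.5391 = 54.9%, × 49 = 26.9

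The total of 60.9 is near the plan's 58, which also allows for 5% annual drop-out. These are progressions and deaths together. They say nothing about who starts another drug within 30 days, and they omit patients who stop for toxicity and then switch.

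**6. A side effect of the ± 5 days.** A contact at day 25 cannot capture days 26 to 30, which the TEAE definition still covers.

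**The case against.** The best defence is that the protocol already says which section governs collection. Section 6.11.11 refers the reader to a separate chapter for, among other things, the AE collection period. The chapter number does not print, but only Chapter 7 covers those topics, and 7.10 is the section in it that sets the period. Section 7.5 likewise uses new anti-tumour therapy as an end point for following unresolved AEs. Sections 6.4 and 6.11.12 describe a contact, not an onset window, and a day-30 call can be limited to pre-switch events. On that reading little next-line toxicity is collected, and what is collected (suspected study-drug SAEs and AESIs) belongs in the tables.

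This makes the problem conditional but does not remove it. The Table 1 row that sites work from has no cut, 6.11.12 applies to all patients, and the TEAE definition does not refer to 7.10.

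Section 5.12.3.2 can also be cited. It bars prohibited drugs up to the safety follow-up visit and other GIST-active therapy during the study, so read strictly nobody switches early. But 7.10, 6.4 and Table 1 all provide for switches, so it is one more text to reconcile.

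Several points limit the consequence, and they stand. AE incidence has no formal test. A patient counts once per SOC or preferred term at worst severity, so a post-switch event changes incidence only if it is a new term or a higher grade. Causality is assessed for every AE, which partly protects treatment-related summaries, though not the all-cause tables.

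**Conclusion.** The inconsistency is real and matters for the safety tables. Next-line toxicity can be counted as TEAEs of the randomised arm if sites record post-switch events under Table 1, 6.4 or 6.11.12, and collection can be uneven between sites. The primary endpoint and the consistency criterion are not affected.

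A reader might infer that about 34 sunitinib and 27 ripretinib patients are exposed to this, and that the sunitinib arm's TEAE rates would therefore be inflated more. The documents do not support that. Those counts are PFS events including deaths, not switchers, and no switch rate or timing is given. The direction is also open. Scheduled scans fall on day 1 of a cycle, when a sunitinib patient on schedule has been off drug for about 42 − 28 = 14 days, so roughly 30 − 14 = 16 days of the window remain when progression is found. A ripretinib patient, dosed continuously, may have close to the full 30. More progressions under sunitinib and a shorter remaining window pull in opposite directions.

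The conclusion assumes that no separate SAP text, beyond what is supplied, redefines TEAEs. Section 9.5.5.1 defers PFS rules to an SAP, but no such deferral is stated for TEAEs.

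**What to change.** Use one end-of-window rule throughout.

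- **9.5.6.1:** define TEAEs as AEs that start or worsen from the first dose to the earlier of 30 days after the last dose and the day before new anti-tumour therapy starts, plus any SAE or AESI after the switch that is suspected to be caused by study drug. Keep the latter in the tables, flagged. Put other post-switch events in the listing. State whether the added SAEs and AESIs are confined to the 30 days, so that switchers and non-switchers are treated alike.
- **6.4, 6.11.12 and the Table 1 AE row:** cross-refer to the 7.10 period, so that the day-30 call asks for events before the switch and, after it, only for suspected study-drug SAEs and AESIs.
- **5.12.3.2:** reconcile its bar on other anti-tumour therapy with the sections that anticipate switching.

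The exception for suspected SAEs and AESIs is needed. A plain cut with everything later in the listing would drop from the tables the events that 7.10 deliberately keeps reportable, including squamous cell carcinoma of skin.

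The cost is wording only. New-therapy information is already collected; the rule needs the start date to be part of it. The downside is small: a few late non-serious study-drug events in switchers move from table to listing.
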